5.5.2 Multiple Measurements within Visit Windows

In the event that more than one assessment falls within a given window, the assessment closest to the target study day will be selected for the by-visit analysis. If two assessments are equidistant from the target study day, then the chronologically last assessment will be used. Exceptions may be made for incomplete assessments, in which case, more complete assessments may be given priority. Details are provided in a separate programming specifications document.

For safety analyses where the extreme values should be selected (e.g., overall post-Baseline minimum, overall post-Baseline maximum, and potentially clinically important values), all

non-missing post-Baseline values should be considered, regardless of whether the value is selected for the by-visit summaries. All assessments will be presented in data listings.

5.6 Missing or Incomplete Date for Last Dose of Study Drug

For subjects with completely missing last dose date, the last dose date will be imputed by the last expected dosing date, defined as the earliest of the following dates: last drug kit dispense date + scheduled dosing interval per protocol, EOT/ET date and the return date of the last dispensed drug kit.

For subjects with partial missing last dose date, the imputation will be compared against the last expected dosing date as defined above. Detailed algorithms will be documented in a separate programming specifications document. The missing or incomplete dates will be displayed in the data listings as reported on the eCRF rather than the imputed dates.

5.7 Missing or Incomplete Dates for Prior or Concomitant Medications

Missing or incomplete medication start or stop dates will be imputed for the purpose of determining whether the medication is taken concomitantly or not (see [Section 11](#) for definition). When the chronological order of medication use relative to the study drug treatment period is unclear due to missing or incomplete date(s), the medication will be considered as concomitant. The imputation algorithms will be detailed in the analysis dataset specification document. The missing or incomplete dates as captured on the eCRF will be displayed in the data listings.

5.8 Missing or Incomplete Date for Adverse Events

Missing or incomplete adverse event (AE) start dates will be imputed for the purpose of determining whether the AEs are treatment-emergent or not (see [Section 12.2](#) for definition). When the chronological order of an AE onset relative to the study drug treatment period is unclear due to missing or incomplete date(s), the AE will be considered as treatment-emergent. The imputation algorithms will be detailed in the analysis dataset specification document. The missing or incomplete dates captured on the eCRF will be displayed in the data listings.

5.9 Missing Severity Assessment for Adverse Events

If the severity is missing for an AE starting on or after the date of the first dose of study drug, then a severity of “Severe” will be assigned. The imputed values for severity assessment will be used for incidence summaries, while the actual values will be used in data listings.

5.10 Missing Relationship to Study Drug for Adverse Events

If the relationship to study drug is missing for an AE starting on or after the date of the first dose of study drug, a causality of “Related” will be assigned. The imputed values for relationship to study drug will be used for incidence summaries, while the actual values will be presented in data listings.

5.11 Character Values of Clinical Laboratory Variables

If the reported value of a clinical laboratory variable cannot be used in a statistical analysis due to, for example, a character string reported for a numeric variable, an appropriately determined coded value may be used in the statistical analysis. The coding algorithms will be detailed in the analysis dataset specification document. The actual values as reported in the database will be presented in data listings.

6. SUBJECT DISPOSITION

The number of sites that screened at least 1 subject, number of sites that enrolled at least 1 subject, and number of subjects enrolled will be tabulated. In addition, the number of subjects enrolled at each site will also be tabulated by Analysis Set.

The number and percentage of subjects who completed the study, discontinued early (all discontinued and by discontinuation reasons including reason due to the COVID-19 public health emergency (PHE), and the reason for discontinuation will be summarized using the Safety Analysis Sets. All subjects excluded from the Safety Analysis Set and the reason(s) for exclusion will be listed.

7. PROTOCOL DEVIATIONS

Protocol deviations will be reviewed periodically over the course of the study. The review process, definition of the deviation categories, and the classification of a deviation as major or minor are detailed in the Protocol Deviation Management Plan. Protocol deviations will also be assessed with respect to relationship to the COVID-19 PHE.

A summary of the number and percentage of subjects with major protocol deviations for each deviation category will be presented for the Safety Analysis Set in three ways: all protocol deviations, COVID-19-PHE related protocol deviations, and non-COVID-19-PHE related protocol deviations.

Three data listings of all protocol deviations, COVID-19-PHE related protocol deviations, and non-COVID-19-PHE related protocol deviations will be provided.

8. DEMOGRAPHICS AND BASELINE CHARACTERISTICS

Demographics and baseline characteristics will be summarized for the Safety Analysis Set using descriptive statistics. Variables include, but are not limited to, age, age group (5-10 years old, 11-15 years old, and 16-20 years old), race, ethnicity, height, weight, BMI, Baseline RSBQ total score, Baseline RSBQ severity (< 35 total score and \geq 35 total score), and Baseline CGI-S score.

Race will also be categorized by White vs. Non-White. The reported age reflects a subject's age at the informed consent date. Baseline characteristics for subjects in ACP-2566-004 will also be summarized using the baseline of the antecedent study separately.

9. MEDICAL HISTORY

Medical history reported terms will be coded with Medical Dictionary for Regulatory Activities (MedDRA), version 23.0 or newer. The subject incidence will be summarized for each system organ class (SOC) and preferred term for the Safety Analysis Set. A subject will be counted only once per SOC or per preferred term for the summary.

A listing of the SOC, preferred term, body system, verbatim for the medical history condition/event, start and stop dates (when available), and an indicator for whether or not the condition is ongoing will be provided.

Rett Syndrome History

The age at Rett syndrome diagnosis, the age at first symptoms noticed, the number and percentage of subjects by *MECP2* gene mutation, and the number and percentage of subjects with more than one *MECP2* mutation (Yes, No) collected on the Rett History eCRF page will be summarized.

Rett syndrome history will be listed.

10. EXTENT OF EXPOSURE AND TREATMENT COMPLIANCE

Extent of exposure and treatment compliance will be summarized as both continuous variables and categorical variables for Safety Analysis set.

10.1 Exposure to Study drug

Duration of exposure to study drug will be calculated for each subject as (last dose date – first dose date + 1). The number and percentage of subjects within each of the following exposure levels in terms of duration of exposure will also be tabulated: <2 weeks (1 to 13 days), 2 to <12 weeks (14 to 83 days), 12 to <26 weeks (84 to 181 days), 26 to <40 weeks (182 to 279 days), and >=40 weeks (280 days or longer).

10.2 Measurement of Treatment Compliance

The study drug is provided in liquid form supplied in a 500 mL bottle. Study drug compliance will be calculated based on the drug accountability and dose modification data as collected on the eCRF. The study drug compliance will be calculated as (the total volume of drug actually taken (in mL) divided by the total volume of drug expected to be taken)*100.

The total volume of drug expected to be taken will be based on the duration of exposure and dosing schedule as in Table 3. However, if there is any dose modification prescribed by the investigator due to intolerance, the total drug expected to be taken will be adjusted accordingly to account for the modified prescribed dose schedule as recorded in the EDC.

The total volume of drug actually taken will be calculated as (total drug dispensed – total drug returned (height in cm of drug remaining converted into volume in mL based on the following conversion [Table 4](#)).

Treatment compliance will be summarized as a categorical variable. The number and percentage of subjects within each of the following compliance levels will be tabulated: <80%, 80 to 120% and >120%.

Details of treatment compliance calculation are provided in a separate programming specifications document.

Table 3 Dosing Schedule and Total Expected Volume Based on Weight at Baseline of the Present Study

| Weight | Dose | Total Daily Dose | Total Expected Volume |
|-----------|------------------|------------------|--|
| 12-20 kg | 30 mL (6 g) BID | 60 mL (12 g) | 60 mL x Number of Days Expected to be Dosed |
| >20-35 kg | 40 mL (8 g) BID | 80 mL (16 g) | 80 mL x Number of Days Expected to be Dosed |
| >35-50 kg | 50 mL (10 g) BID | 100 mL (20 g) | 100 mL x Number of Days Expected to be Dosed |
| >50 kg | 60 mL (12 g) BID | 120 mL (24 g) | 120 mL x Number of Days Expected to be Dosed |

BID = twice daily

Table 4 Conversion of Height of Remaining Liquid (cm) into Volume (mL).

| Height of Remaining Liquid (cm) | Estimated Volume (ml) | Height of Remaining Liquid (cm) | Estimated Volume (ml) |
|---------------------------------|-----------------------|---------------------------------|-----------------------|
| 0.5 | 18 | 7.0 | 248 |
| 1.0 | 35 | 7.5 | 266 |
| 1.5 | 53 | 8.0 | 283 |
| 2.0 | 71 | 8.5 | 301 |
| 2.5 | 89 | 9.0 | 319 |
| 3.0 | 106 | 9.5 | 336 |
| 3.5 | 124 | 10.0 | 354 |
| 4.0 | 142 | 10.5 | 372 |
| 4.5 | 159 | 11.0 | 389 |
| 5.0 | 177 | 11.5 | 407 |
| 5.5 | 195 | 12.0 | 425 |
| 6.0 | 212 | 12.5 | 443 |
| 6.5 | 230 | 13.0 | 460 |

11. PRIOR, CONCOMITANT, AND POST-TREATMENT MEDICATION

Prior medication is defined as any medication with stop dates prior to the date of the first dose of double-blind study drug from study ACP-2566-003. Concomitant medication is defined as any medications that are ongoing at the first dose of study drug or with a start date between the dates of the first and last doses of study drug, inclusive. Post-treatment medication is defined as any medication with a start date after the date of the last dose of study drug. Medications will be coded using WHO Drug Global Dictionary March 2020 or newer version.

The number and percentage of subjects taking prior, concomitant and post-treatment medications will be tabulated separately by each drug class (ATC Level 3) and medication preferred term, treatment group of the antecedent study and overall for Safety Analysis Set. Multiple medication usage by a subject in the same category will be counted only once. Listings of the prior, concomitant and post-treatment medications will also be provided.

COVID-19 Infection Related Medications

Concomitant medication analyses described above will also be tabulated and listed by relationship to COVID-19 Infection (Not related to COVID-19 Infection vs. Related to COVID-19 Infection).

12. EFFICACY ANALYSES

Unless otherwise specified, all efficacy analyses will be performed using the Safety Analysis Set. No hypothesis testing is planned. Descriptive summaries of all efficacy endpoints will be presented.

12.1 Efficacy Variables

Secondary Efficacy Endpoints

- RSBQ total score – change from Baseline to Weeks 2, 12, 26, and 40
- CGI-I score at Weeks 2, 12, 26, and 40 (assessing improvement from the Baseline of the present study)

Change from Baseline to Weeks 2, 12, 26, and 40 in:

- CSBS-DP-IT Social
- Overall Quality of Life Rating of the ICND
- RTT-HF score
- RTT-AMB score
- RTT-COMC score
- RTT-VCOM score
- CGI-S score
- RTT-CBI total score (items 1-24)
- ICND total score

Response rate based on CGI-I at Weeks 2, 12, 26, and 40

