2.2.1 Secondary Endpoints

The secondary endpoints for this study are:

- Rett Syndrome Behaviour Questionnaire (RSBQ) total score – Change from Baseline to Week 40
- Clinical Global Impression–Improvement (CGI-I) Score at Week 40 (assessing improvement from Baseline of the present study)

Change from Baseline to Week 40 in:

- Communication and Symbolic Behavior Scales-Developmental Profile™ Infant-Toddler Checklist – Social Composite Score (CSBS-DP-IT Social)
- Overall Quality of Life Rating of the Impact of Childhood Neurologic Disability (ICND) Scale
- Rett Syndrome Clinician Rating of Hand Function (RTT-HF)
- Rett Syndrome Clinician Rating of Ambulation and Gross Motor Skills (RTT-AMB)
- Rett Syndrome Clinician Rating of Ability to Communicate Choices (RTT-COMC)
- Rett Syndrome Clinician Rating of Verbal Communication (RTT-VCOM)
- Clinical Global Impression–Severity (CGI-S)
- Rett Syndrome Caregiver Burden Inventory (RTT-CBI) Total Score (items 1-24)
- Impact of Childhood Neurologic Disability (ICND) Scale Total Score

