4.4.2 Handling of Subject Discontinuation During the Treatment Period

Unless the subject has withdrawn consent (or the LAR has withdrawn consent on behalf of the subject) to be contacted for this study, every reasonable effort should be made to complete Visit 5 and the safety follow-up (as outlined in [Table S-2](#)) if a subject discontinues prematurely for any reason. All information will be reported on the applicable pages of the electronic case report form (eCRF).

If a subject is discontinued from the study because of an AE, every reasonable attempt should be made to follow the subject until the AE resolves or until the Investigator deems the AE to be chronic or stable. For subjects who continue to be followed for safety, SAEs should continue to be reported as described in [Section 7.3.2](#). All SAEs will continue to be followed until such events have resolved or the Investigator deems them to be chronic or stable.

Pharmacokinetic samples will also be collected, if possible, at any ET visit or the visit immediately following any SAE or following any AE leading to discontinuation, even if it is an unscheduled visit.

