6.1.4 Impact of Childhood Neurologic Disability (ICND) Scale

The Impact of Childhood Neurologic Disability (ICND) scale was developed to evaluate the impact that a child's condition has on the child's and the family's everyday life at the present time and during the previous 3 months (Camfield et al. 2003). The parent or other caregiver evaluates the effect of a condition or health problem on 11 aspects of the child's or the family's life as "A lot", "Some", "A little", "Not at all", or "Does not apply". The four conditions or health problems are 1) inattentiveness, impulsivity, or mood, 2) ability to think and remember, 3) neurologic or physical limitations, and 4) epilepsy.

The caregiver then rates overall quality of life of the subject by responding to the following: "Please rate your child's overall 'Quality of Life' on the scale below. Choose the number which you feel is best and circle it". The choices range from 1 ("Poor") to 6 ("Excellent").

The assessment will be administered at Baseline and Visit 5.

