6.1.9 Rett Syndrome Caregiver Burden Inventory (RTT-CBI)

The RTT-CBI is a syndrome-specific, caregiver-completed questionnaire that is based on the Caregiver Burden Inventory designed for Alzheimer's disease ([Lane et al. 2017](#); [Novak and Guest 1989](#)). The scale is intended to directly address caregiver burden and indirectly assess the significance of treatment effects on function in the context of activities of daily living. Caregivers rate how often a given statement describes their feeling or experience. Frequency ratings are on a 5-point Likert scale including: 0-never; 1-rarely; 2-sometimes; 3-frequently and 4-nearly always. As in the original Caregiver Burden Inventory, the RTT-CBI has 24 negatively worded items (items 1 through 24) yielding a total score up to 96. The RTT-CBI also includes 2 positively worded items (items 25 and 26) that comprise the Optimism Index ([Lane et al. 2017](#)). In this study, as in the 2 previous studies of trofinetide in Rett syndrome, the total score is defined as the total Burden score (items 1-24).

The RTT-CBI will be completed at Baseline, Visit 3, and Visit 5.

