5.5 Analysis Visit Windows

Efficacy, safety, and PK assessments will be summarized by analysis visit as presented in Table 2 below.

Table 2 Analysis Visit Windows

| Analysis Visit | Target Study Day | Study Day Interval |
|------------------------|------------------|--------------------|
| Baseline (Day 1) | 1 | ≤ 1 |
| Day 1 Post First Dose* | 1 | 1 |
| Week 2 | 15 | 2 – 49 |
| Week 12 | 85 | 50 – 133 |
| Week 26 | 183 | 134 – 231 |
| Week 40 | 281 | 232 – 310 |

*For ECG and PK assessments only; other assessments post-first dose on Day 1 will go to the Week 2 analysis visit window.

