5.5.1 Unscheduled Assessments

Both Scheduled and Unscheduled assessments, including the assessments at early termination visits, will be included for planned timepoint analyses based on the above analysis visit windowing rules. All assessments will be presented in data listings.

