13. METHODS OF EFFICACY ANALYSES

13.1 Analysis of Continuous Efficacy Endpoints

Descriptive statistics for all efficacy endpoints listed in [Section 12.1](#) will be tabulated by treatment group of the antecedent study. The summaries of the change from baseline results will be presented in two ways (main analysis and exploratory analysis) as specified in [Section 5.1](#).

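### SAP 12.1 lists ICND change at Weeks 2, 12 and 26 and RTT-CBI change at Weeks 2 and 26, where neither scale is scheduled, so those rows would describe essentially only early leavers

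*SAP*

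**What the plan says.** **Endpoints and tables.** SAP 12.1 uses one heading, "Change from Baseline to Weeks 2, 12, 26, and 40 in", for nine endpoints, among them the ICND quality-of-life rating, the ICND total and the RTT-CBI total. It makes no exception for any scale. SAP 13.1 then commits to "Descriptive statistics for all efficacy endpoints listed in" Section 12.1, against both baselines described in SAP 5.1. The protocol defines the same endpoints (Section 2.2.1) as "Change from Baseline to Week 40 in". SAP 19 declares no departure from the protocol analyses.

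**Collection.** Protocol 6.1.4 on ICND: "The assessment will be administered at Baseline and Visit 5". Protocol 6.1.9: "The RTT-CBI will be completed at Baseline, Visit 3, and Visit 5". Protocol Table S-2 and the SAP's own schedule (21.1) agree. Visit 3 is Week 12, and Visit 5 is Week 40, end of treatment or early termination.

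**Early leavers and windows.** For subjects who stop early, Protocol 4.4.2 says "every reasonable effort should be made to complete Visit 5 and the safety follow-up". SAP 5.5: "Efficacy, safety, and PK assessments will be summarized by analysis visit as presented in Table 2 below". SAP 5.5.1: "Both Scheduled and Unscheduled assessments, including the assessments at early termination visits, will be included for planned timepoint analyses", by the study-day intervals of Table 2.

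**The concern.** The SAP names visits for these three scores at which the study does not collect them, and its windowing rule fills the resulting gaps with a selected group. An ICND completed at withdrawal on day 100 would be printed as a Week 12 value. The ICND rows at Weeks 2, 12 and 26 would then be essentially leavers, while the Week 40 row would be completers plus anyone leaving after day 231. These are largely different people shown as one time course. A difference between Week 26 and Week 40 could reflect who left rather than change within subjects.

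The printed n shows that an early row is small, but not that it consists of leavers. SAP 5.1 also attaches a 95% confidence interval to every efficacy summary, which gives such a row the look of an ordinary planned visit.

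For RTT-CBI only Weeks 2 and 26 are affected; Weeks 12 and 40 rest on scheduled data.

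**Working it through.** **1. Which listed weeks can receive a scheduled value?** The inputs are the analysis windows (SAP Table 2), the visit windows (schedule of assessments) and the collection visits (Protocol 6.1.4 and 6.1.9). Target days are 15, 85, 183 and 281. The window borders are the midpoints: (15+85)/2 = 50, (85+183)/2 = 134, (183+281)/2 = 232. Visit 3 (day 85 ± 7) falls on days 78–92, and Visit 5 (day 281 + 7) on days 281–288.

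| Score | Week 2 (days 2–49) | Week 12 (50–133) | Week 26 (134–231) | Week 40 (232–310) |
|---|---|---|---|---|
| ICND quality of life | none | none | none | Visit 5 |
| ICND total | none | none | none | Visit 5 |
| RTT-CBI total | none | Visit 3 | none | Visit 5 |

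Rows without scheduled data: 3 + 3 + 2 = 8 of 3 × 4 = 12. Shown against both baselines, these become 16 of 24. As a check, RSBQ, which is collected at every visit, fills all four windows.

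**2. Could a mistimed visit fill the gaps?** Visit 3 would have to be at least 85 − 49 = 36 days early to reach Week 2, or 134 − 85 = 49 days late to reach Week 26. A Visit 5 that is not an early termination would have to be at least 281 − 231 = 50 days early. A questionnaire completed on Day 1 after the first dose would also go to Week 2 (Table 2 footnote). These are strays, so the rows hold essentially only early-termination values.

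**3. How many subjects?** The documents give no dropout rate, so this step rests on assumptions: N = 180 (the planned maximum), total dropout p by day 280, constant hazard, and every leaver assessed on the day of leaving. With S(t) = (1 − p)^(t/280), the number of leavers in a window of days a to b is 180 × [S(a−1) − S(b)].

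For p = 0.30, Week 2: 180 × [S(1) − S(49)] = 180 × (0.9987 − 0.9395) = 10.7.

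| Dropout p | Days 2–49 | Days 50–133 | Days 134–231 | Days 232–280 | Week 40 row = completers + last window |
|---|---|---|---|---|---|
| 10% | 3.2 | 5.5 | 6.2 | 3.0 | 162 + 3.0 = 165.0 |
| 30% | 10.7 | 17.2 | 17.8 | 8.1 | 126 + 8.1 = 134.1 |
| 50% | 20.1 | 29.9 | 27.9 | 11.6 | 90 + 11.6 = 101.6 |

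The first three columns are the ICND rows at Weeks 2, 12 and 26. RTT-CBI at Weeks 2 and 26 has the same counts as ICND at those weeks. If exits are spread uniformly instead, the first three windows hold 3.1/5.4/6.3, 9.3/16.2/18.9 and 15.4/27.0/31.5. If only half of the leavers are assessed, the early rows halve: about 2/3/3 at 10% and 10/15/14 at 50%.

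**4. Thyroid tests.** SAP 14.2 places TSH, free T3 and free T4 at Visits 1 and 5, yet summarizes laboratory change at every post-Baseline visit. The same windowing would put leavers' thyroid values into the early rows.

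**The case against.** The strongest reply is that the heading in 12.1 is shorthand over nine endpoints, six of which really are collected at every visit, and that a programmer would drop rows a scale does not have. Protocol 9.5.3 uses similar shorthand when it promises summaries by timepoint. SAP 5.5.1 speaks of planned timepoints, and Weeks 2, 12 and 26 are not planned for ICND. The table shells and windowing specifications are in separate documents, so the misleading table is a prediction. It remains one, but 12.1 names the four weeks explicitly and 13.1 allows no exception. The text should not depend on an unwritten correction.

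The limit on consequence stands. These are secondary, descriptive endpoints with no hypothesis testing, the protocol's Week 40 endpoint is untouched, and all assessments are listed.

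Three smaller points also stand in part:
- The subject counts are assumptions. They are split further by antecedent treatment group. They may overstate ICND total, which is missing if any one of the four health-problem scores is missing (SAP 5.2.11).
- The thyroid case is weaker, because 14.2 names no weeks and states the two-visit schedule itself. The windowing route is nevertheless the same.
- Early-termination values enter the windows of every scale, so footnotes on particular rows are optional.

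**Conclusion.** The concern holds. Eight of the 12 post-baseline rows that SAP 12.1 lists for these three scores have no scheduled collection; this follows from the documents alone. Read literally, SAP 5.5 and 5.5.1 fill those rows with early leavers under planned-visit labels. How many subjects that means depends on dropout: on the stated assumptions, from about 3, 6 and 6 in the ICND rows at Weeks 2, 12 and 26 (10% dropout) to about 20, 30 and 28 (50%). The defect should be corrected, but its reach is limited to descriptive summaries. No error rate, primary safety result or Week 40 estimate changes. Whether the tables would in fact show these rows cannot be settled without the shells.

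**What to change.** - **SAP 12.1:** list both ICND scores at Week 40 only, and RTT-CBI total at Weeks 12 and 40 only. The three scores then have 4 post-baseline rows instead of 12, all with scheduled data.
- **SAP 5.5.1:** state that an assessment is windowed only to visits at which it is scheduled, that the Table 2 intervals still apply, and that earlier early-termination values are not moved into Week 40.
- **Remaining early-termination values:** show them in the listings, or in a separate early-termination row with n and the median and range of study day. Such a row pools exits at different times, so the study-day range is needed.
- **SAP 14.2:** apply the same condition to the by-visit tables for TSH, free T3 and free T4. Their last, minimum and maximum post-Baseline summaries stay as they are.
- **Optional footnotes:** give the number of early-termination values in the Week 40 row (leavers after day 231) and in the RTT-CBI Week 12 row (leavers on days 50–133 whose early-termination value is selected).

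The core cost is one wording change in 12.1, one sentence in 5.5.1 and one programming condition. The separate row and the footnotes add a little table work and can be left out. No data are lost, since all assessments are already listed, and the Week 40 row does not change.
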